9.4 Exploratory Efficacy Analyses

The following exploratory analyses will be performed on these additional efficacy outcomes:

1. Pain Relief Score after first dose over time
2. Pain Intensity Score after the first dose over time (based on NRS)
3. Pain Intensity Difference (PID, NRS) after first dose over time
4. Peak pain relief score
5. Peak pain intensity difference
6. Time to request the first dose of rescue medication
7. Time to peak pain relief score
8. Time to peak pain intensity difference

Pain relief scores, pain intensity scores, and pain intensity difference scores over time will be analyzed at each time point using the same ANCOVA model described for the primary endpoint, TOTPAR4. Peak pain relief score and peak pain intensity difference will also be analyzed using the same ANCOVA model described for the primary endpoint.

Time to peak pain relief score and time to peak pain intensity difference be presented using Kaplan-Meier plots. Medians will be compared across the groups using Wilcoxon Log-rank test, and Hazard Ratios (HR) will be compared across the groups using Cox Hazard Ratio model. The summaries will include quartiles and HR and their corresponding 95% confidence intervals along with the p-values. Please see [Appendix B](#) for details on the determination of event and censoring time points. Note that alpha levels for exploratory analyses are not adjusted for multiple comparisons.

10. SAFETY ANALYSES

The following safety data will be collected: Adverse events, clinical laboratory parameters, and vital signs. All safety analyses will be based on the Safety population. Clinically relevant abnormal values (per investigator's judgment) must be recorded as adverse events.

Safety and tolerability will be assessed throughout the study by monitoring and evaluating treatment emergent adverse events (TEAEs), including any complications resulting from the study drug administration, and changes in vital signs and in clinical safety laboratory test and PE findings. All safety and tolerability endpoints will be summarized by treatment. Baseline for all safety endpoints will be defined as the last recorded observation before the administration of the study drug. Safety measures, including AEs, clinical safety laboratory tests, vital signs, PEs, and concomitant medication usage, will be summarized descriptively. For quantitative variables, descriptive statistics, including number of observations, means, Q1, medians, Q3, SDs, and

ranges, will be provided for the values themselves as well as for the changes from Baseline by treatment group at each study visit. Qualitative variables will be summarized using counts and percentages in each treatment group at each study visit.

10.1 Adverse Events

Definition of adverse events

An adverse event is any untoward medical occurrence in a subject enrolled in a clinical trial. An adverse event can therefore be any unfavorable and unintended sign (e.g., an abnormal laboratory finding), symptom, or disease temporally associated with the use of a medicinal product, whether or not considered related to the medicinal product.

Pre-existing diseases or conditions occurring before enrollment are not considered to be adverse events unless there is an untoward change in intensity, frequency, or quality after enrollment.

LoE, as such, is not considered to be an adverse event while its consequences (e.g., deterioration of the treated disease) are considered to be an adverse event.

A newly diagnosed pregnancy of an enrolled female subject will not be considered an adverse event itself unless it is suspected that the trial treatment interacted with a contraceptive method. In this case, the pregnancy will be considered an adverse event. A congenital anomaly as an outcome of this pregnancy will be considered a serious adverse event (SAE).

All newly diagnosed pregnancies of enrolled female subjects must be reported to the CRO/sponsor's Drug Safety department within 24 hours after first knowledge. These pregnancies will be documented using a Pregnancy Reporting Form with all available information provided and followed up to determine the outcome post parturition.

For newly diagnosed pregnancies of partners of enrolled subjects, a reasonable attempt (i.e., due diligence) must be made to report the pregnancy to the CRO/sponsor's Drug Safety department within 24 hours after first knowledge.

Definition of serious adverse events

An SAE is any untoward medical occurrence that at any dose:

- Results in death.
- Is life-threatening.
- Requires inpatient hospitalization or prolongation of existing hospitalization.
- Results in persistent or significant disability/incapacity.
- Is a congenital anomaly/birth defect.
- Is considered a clinically important medical event. The medical concepts included in Appendix A should be taken into account when applying this seriousness criterion.

An elective hospital admission, e.g., for pre-planned surgery, will not be considered an SAE if documented at enrollment. Short-lasting (<24 hours) hospital admissions, e.g., for clinical check-ups, not meeting any of the other above mentioned criteria will also not be considered SAEs.

Analysis of adverse events

Adverse events will be coded to System Organ Class (SOC) and preferred term using MedDRA (version 19.0). The tabular summaries will be provided for AEs, with the number and percentage of subjects reporting each type of event presented by each treatment group and placebo. If a subject reports the same preferred term more than once, it is counted only once within that category. Further, for a given tabulation, the preferred term will only be counted once at its worst severity and strongest relationship to treatment.

Any adverse event which occurs after first administration of the IMPs or pre-existing adverse event which worsens (adverse change in intensity, frequency, or quality) after first administration of the IMPs compared to the complaint present before first intake of the IMPs is considered as a TEAE.

TEAEs will be summarized for each treatment group by SOC and Preferred Term. Additional summaries by time to onset, duration, intensity, relationship to IMP (Related/Not Related), outcome, expectedness, and countermeasures will also be produced. Events reported as "Conditional/Unclassified", "Assessable/Unclassifiable", "Possible", "Probable/Likely", or "Certain" will be included in the Related category. Events reported as "Unlikely Related" or "Not Related" will be included in the Not Related category. Expectedness will be assessed by the sponsor. An unexpected adverse event is one where the nature or intensity is not consistent with the information in the investigator's brochure. Definition of intensity (mild, moderate, or severe) and countermeasures (none, newly started medication, trial discontinuation, or other) is described in the protocol Section 12.3.1.

Subjects with SAEs will be summarized and additionally listed. Special attention will be given to those subjects who discontinue treatment due to an adverse event or who experience a severe adverse event or SAE.

The incidence of all adverse events and TEAEs leading to premature discontinuation from treatment will be presented descriptively.

Selected subset of adverse events

Selected adverse events of interest will be summarized in a separate table:

- Nausea
- Vomit
- Abdominal Pain
- Gastrointestinal Bleeding
- Dizziness
- Hypotension

10.2 Clinical Laboratory Evaluation

Clinical laboratory parameter data (clinical chemistry, hematology, and coagulation) and urinalysis results will be descriptively summarized by type of laboratory test and time point.

Both conventional and SI units are provided and will be summarized in separate tables and listings.

Descriptive statistics for the chemistry and hematology values will be presented. Continuous laboratory parameters will be summarized by n (%), Mean, Q1, Median, Q3, SD and (Min, Max). Categorical laboratory parameters will be summarized by treatment group for each target visit using counts and percent of subjects in each category. Missing n (%) will be indicated in all tables. Listings of laboratory parameter results will be presented.

10.3 Vital Signs

Descriptive statistics will be calculated for each parameter of the vital signs (diastolic blood pressure, systolic blood pressure, pulse rate, and respiratory rate) collected at Visit 1 and Visit 2. For the summary tabulations of vital signs at baseline, baseline will be defined as the last non-missing value prior to the first dose of study drug. Change from baseline in these vital signs will also be calculated and summarized as the value at Visit 2 minus the baseline value.

10.4 Prior and Concomitant Medications

Verbatim terms on case report forms will be mapped to Anatomical Therapeutic Chemical (ATC) class and Generic Drug Names using the World Health Organization (WHO) dictionary (version March 2016).

For the purposes of data reporting by the site, all medication used 14 days prior to enrollment and up to the time of surgery is considered prior medication. Concomitant medication is all medication not stopped before start of surgery or newly added thereafter. Prior medications and concomitant medications will be summarized separately for each treatment by WHO ATC level 1 term, ATC level 3 term and Preferred Term (generic name) with frequency and percentage of subjects in each dosing arm using each prior medication and each concomitant medication. At each level of subject summarization, a subject is counted once if he/she reported one or more medications at that level. Each summary will be ordered alphabetically by each level of ATC class and generic drug name within each level of ATC class. Prior and Concomitant medications will also be listed separately with these elements as well as the verbatim drug name.

The overall summary and subsets of prior and concomitant medications will be provided for the Safety Set, FAS and PPS.

11. CHANGES TO PROTOCOL-SPECIFIED ANALYSES

For subject's dental history, summary of that data as suggested by Section 14.4 of the study protocol will not be provided but instead will be displayed in a by-subject data listing.

Two sensitivity analyses have been added to this SAP beyond what is stated in the protocol to address the specific concern when rescue medication is given prior to the scheduled assessment time. Clearly, once rescue medication is given the pain levels will drop significantly and measurements post rescue medication are excluded from the analyses. The sensitivity analyses stated in Section 8.3 and 9.2.1 of this document will enable us to include subjects with rescue

medication at the subsequent assessment time point while the primary analyses and the primary endpoint remain the same as stated in the protocol.

In addition, 4 exploratory efficacy endpoints have been added to the analyses: peak pain relief score, peak pain intensity difference score, time to peak pain relief score, and time to peak pain intensity difference score, as stated in Section 8.1.3 and further described in Section 9.4. Each of these is considered a routine endpoint in dental study models and each was added for completeness of the analyses.

APPENDICES

[figure not shown]
Appendix A: Definitions for Efficacy Endpoints

1. Pain Intensity and Numerical Rating Scale (NRS)

11-point Numerical Rating Scale (NRS) is used to evaluate pain intensity.

Pain Intensity Rating Scale

Please rate your pain by selecting the one number that best describes how much pain you have right now:

Pain intensity: Subjects will be asked to assess their current pain by selecting a number corresponding to their pain, with anchors at 0 for “no pain” and 10 for “pain as bad as you can imagine”. The subjects will be asked to answer the following question:

“Please rate your pain by selecting the one number that best describes how much pain you have right now”.

Pain intensity will be categorized as:

- None NRS score of 0
- Mild NRS score of ≥ 1 and < 5
- Moderate NRS score of ≥ 5 and ≤ 6
- Severe NRS score of ≥ 7

NRS pain scores will be assessed before the first dose of IMPs, and 15, 30, 45, 60, and 90 minutes (± 2 minutes), and 2, 3, 4, 5, 6, 7, 8, 16, and 24 hours (± 6 minutes) after the first dose of IMPs.

2. Pain Relief and Verbal Rating Scale (VRS)

The subject's pain relief will be assessed using a 5-point Verbal Rating Scale (VRS) by completion of the following statement.

"My relief from starting pain is"

- None (0)
- A little (1)
- Some (2)
- A lot (3)
- Complete (4)

Pain relief will be assessed 15, 30, 45, 60, and 90 minutes (± 2 minutes), and 2, 3, 4, 5, 6, 7, 8, and 16 hours (± 6 minutes) after administration of the first dose of IMPs.

3. Total Pain Relief at 4, 6, and 8 hours (TOTPAR4, TOTPAR6, and TOTPAR8)

Total Pain Relief (TOTPAR) will be defined as $\sum PR_t \times$ [time (hours) elapsed since previous observation] where PR_t is the Pain Relief at time point t in comparison to the assessment before administration of IMPs. The TOTPAR will be calculated at 4, 6, and 8 hours.

4. Peak Pain Relief

Peak pain relief will be defined as the maximum pain relief score for the subject over the 16 hours after administration of the first dose of IMPs, but prior to the intake of any rescue medications.

5. Pain Intensity Difference (PID)

Pain Intensity Difference (PID_t) will be defined as the difference between baseline pain intensity and pain intensity at time point t (e.g., baseline score - time point t score). The PID (11-point NRS) compared to baseline at 15, 30, 45, 60, and 90 minutes, and at 2, 3, 4, 5, 6, 7, 8, and 24 hours will be calculated.

6. Summed Pain Intensity Difference (SPID)

Summed Pain Intensity Difference (SPID) will be defined as $\sum PID_t \times$ [time (hours) elapsed since previous observation]. The SPID at 4, 6, 8, and 24 hours post-dose will be calculated.

7. Peak Pain Intensity Difference

Peak pain intensity difference will be defined as the maximum pain intensity difference for the subject over the 24 hours after administration of the first dose of IMPs, but prior to the intake of any rescue medications.

8. Subject's Global Evaluation of the Treatment (Likert Scale)

The subject's overall impression (overall assessment) of the analgesic efficacy of the IMPs will be obtained at 8 hours after the first dose of IMPs or before first intake of rescue medication (whichever happens first) and at 24 hours after the first dose of IMPs. Subjects will be asked the following question and will be requested to also record the time at which it was answered:

"How would you rate the study medication you received for pain?"

- Excellent (4)
- Very good (3)
- Good (2)
- Fair (1)
- Poor (0)

9. Time to Achieve a 50% Reduction of Baseline Pain

The subject's 50% reduction of starting pain will be assessed by answering the following statement with YES or NO:

"My starting pain is at least half gone"

The subject should be reminded that each assessment should be performed independently of previous assessments.

10. Time to Onset of First Perceptible and Meaningful Pain relief

At the time of dosing with the IMPs, the investigator will start 2 stopwatches for each subject. The subject will be instructed to stop the first stopwatch at the time of first perceptible pain relief and the second stopwatch at the time when they first experience meaningful pain relief. The definitions of the perceptible and meaningful pain relief are as follows:

Time to onset of first perceptible pain relief

When the subject begins to feel any pain-relieving effect from the IMPs.

Subject instruction:

"I would like you to stop the stopwatch when you first feel any pain relief whatsoever. This does not mean you feel completely better, although you might, but when you first feel any difference in the pain that you have had."

Time to onset of meaningful pain relief

When the subject feels their pain relief is meaningful to them.

Subject instruction:

“I would like you to stop the stopwatch when you have meaningful pain relief. That is, when the relief is meaningful to you.”

11. Time to Request and Intake of First Rescue Medication

The day/actual time of ibuprofen (and of ketorolac if needed) request and the day/actual time and amount of ibuprofen intake (or ketorolac administration) will be documented in the CRF and the source document(s). The time from administration of IMP to the first dose of rescue medication will be calculated.

12. Time to Peak Pain Relief and Peak Pain Intensity Difference Scores

The first day/time where the subject reaches their maximum pain relief and their maximum pain intensity difference, as described in items 4 and 7 above, respectively, will be considered the event times for these two endpoints.

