1.8 Schedule of events

Procedure	Visit 1 (Enrollment Visit)	Visit 2 (Allocation Visit)	Visit 3 (End-of- treatment Visit)	Visit 4 (Final Visit [phone call or on-site visit])
	Day -10 to -1	1	2	14
Obtain informed consent	X			
Distribute subject trial card	X			
Evaluate inclusion/exclusion criteria	X	X		
Obtain radiological confirmation of impacted third molars (if not available from previous visit)	X	(X)		
Record demographic data (date of informed consent, sex, age, race, ethnicity, weight, height) and smoking status	X			
Record medical and dental history	X			
Perform physical examination ^a	X			
Take blood samples for clinical laboratory parameter assessments and urine for urinalysis ^{a, b}	X			
Record vital signs (pulse rate, systolic and diastolic blood pressure, respiratory rate)	X	X		
Perform urine pregnancy test (female subjects with childbearing potential only)	X	X		
Record prior medication	X			
Record concomitant medication	X	X	X	
Schedule appointment for dental surgery	X			
Record details of local anesthesia and dental surgery (3rd molar extractions)		X		
Allocate subject to treatment group		X		
Dispense IMPs		X		
Handout 2 stopwatches and a pain assessment booklet to each subject		X		
Record administration of IMPs		X		
Record pain intensity (NRS) ^c		X	X	
Record pain relief (5-point VRS) ^d		X		
Record pain at least half gone (YES/NO) ^e		X	X	
Transfer stopwatch times ^f to CRF		X		
Document IMP intake and rescue medication use (request/intake)		X	X	
Dispense IMPs to be taken at home and rescue medication		X		

Procedure	Day	Visit 1 (Enrollment Visit)	Visit 2 (Allocation Visit)	Visit 3 (End-of- treatment Visit)	Visit 4 (Final Visit [phone call or on-site visit])
		-10 to -1	1	2	14
Collect IMPs and rescue medication and perform drug accountability				X	
Record subject's global evaluation of the treatment (5-point Likert scale) ^g			X	X	
Record all adverse events			X	X	X

a) Physical examination results and clinical laboratory parameter and urinalysis data must be available at the latest at Visit 2.

b) Clinical laboratory parameter assessments will be performed by contracted local certified clinical laboratories.

c) NRS pain scores will be assessed before the first dose of IMPs, and 15, 30, 45, 60, and 90 minutes (± 2 minutes), and 2, 3, 4, 5, 6, 7, 8, 16, and 24 hours (± 6 minutes) after the first dose of IMPs.

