 - Hand out sufficient rescue medication (ibuprofen 400 mg) to cover 24 hours of treatment of dental pain if insufficiently resolved by the intake of IMPs.
 - Hand out an information sheet to the subject with the protocol directions and contact details.
 - Hand out a booklet and ask the subject to document at home:
 - Pain intensity and pain relief at 16 hours.
 - The intake of the third dose of IMPs.
 - Any use of rescue medication.
 - Any use of other medication.
 - Adverse events they might experience.
 - Check that the subjects are in a condition to leave the site.
 - Before subjects leave the site they should be reminded that tramadol-containing products, may impair the mental and/or physical abilities required for the performance of potential hazardous tasks such as driving a car or operating machinery.
 - Ask the subject to come to the site on the next day at a pre-set time (24 hours after first IMP intake) for Visit 3.

Dental clinics must have an emergency kit according to local regulations (Norma Oficial Mexicana NOM-005-SSA3-2010). An emergency crash cart will be mandatory at each research facility any time an IMP is being administered.

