12.2.1.3 Total Pain Relief

Total Pain Relief (TOTPAR) will be defined as $\sum PR_t \times$ [time (hours) elapsed since previous observation] where PR_t is the Pain Relief at time point t in comparison to the assessment before administration of IMPs (Max and Laska 1991).

The TOTPAR will be calculated at 4, 6, and 8 hours.

12.2.1.4 (Summed) Pain Intensity Difference

Pain Intensity Difference (PID_t) will be defined as the difference between baseline pain intensity and pain intensity at time point t, and Summed Pain Intensity Difference (SPID) defined as $\sum \text{PID}_t \times$ [time (hours) elapsed since previous observation] (Max and Laska 1991).

The PID (NRS) compared to baseline at 15, 30, 45, 60, and 90 minutes, and at 2, 3, 4, 5, 6, 7, 8, and 24 hours will be calculated.

The Summed Pain Intensity Difference (SPID) at 4, 6, 8, and 24 hours post-dose will be calculated.

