14.5.4 Analysis of additional efficacy outcomes

The pain intensity scores (NRS) at all the time points (see Section 1.8) after the first dose of IMPs will be analyzed by an ANCOVA model with treatment, site, and baseline pain as covariates.

Pain relief expressed as Total Pain Relief after 6 hours and after 8 hours (TOTPAR6, TOTPAR8) will be analyzed with the same ANCOVA model and missing data handling as the primary analysis.

The specification of the statistical analysis of the following additional efficacy outcomes including statistical analysis models, formal statistical tests, and further specifications in detail will be provided in the statistical analysis plan:

- Pain intensity score reductions (Pain Intensity Difference [PID], NRS) for each time point after the first dose of IMPs.
- Summed Pain Intensity Difference (SPID) at 4, 6, 8, and 24 hours after the first dose of IMPs.
- Pain relief scores for each time point after the first dose of IMPs.

-
- Time to onset of first perceptible pain relief (Stopwatch 1).
 - Time to onset of meaningful pain relief (Stopwatch 2).
 - Time to achieve a 50% reduction in baseline pain (pain at least half gone).
 - Time to request the first dose of rescue medication.
 - Time to first intake of rescue medication.
 - Subject's global evaluation of the treatment (5-point Likert scale) 8 hours or before first intake of rescue medication (whatever the first) and 24 hours after the first dose of IMPs.

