8.3 Handling of Dropouts or Missing Data

Diligent attempts will be made to limit the amount of missing data in the pain relief assessments used to determine the primary efficacy endpoint. Efforts will be made to encourage but not to enforce subjects to not start rescue medication intake if not needed. Assessments with missing date/time of evaluation will be considered unreliable and removed from all analyses and treated as missing values. Assessments made after the subject's first dose of rescue medication will be considered missing values and excluded from the analyses. Other than the methods outlined below for TOTPAR4, TOTPAR6, and TOTPAR8, no imputations will be performed to replace missing values for any of the other endpoints; those missing values will be left as missing.

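### The PID time lists leave out 16 hours although pain is scored then; on the listed times the 24-hour reading carries two thirds of the SPID24 time weight

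*SAP*

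**What the plan says.** Pain intensity on the 11-point NRS is scheduled up to 24 hours. Footnote c of the protocol's schedule of events (section 1.8) gives the later times as "2, 3, 4, 5, 6, 7, 8, 16, and 24 hours", and SAP Appendix A item 1 has the same schedule. Among the items the subject records in the booklet at home, protocol section 11.1.2.1 names "Pain intensity and pain relief at 16 hours".

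The PID lists are shorter. SAP Appendix A item 5 has PID "compared to baseline at 15, 30, 45, 60, and 90 minutes, and at 2, 3, 4, 5, 6, 7, 8, and 24 hours". Protocol section 12.2.1.4 has the same list, ending "and at 2, 3, 4, 5, 6, 7, 8, and 24 hours will be calculated". Neither gives a reason for leaving out 16 hours, and SAP section 11 does not record it as a change.

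Other text points the other way. Protocol section 14.5.4 plans PID "for each time point after the first dose of IMPs", and SAP section 9.4 says that "pain intensity difference scores over time will be analyzed at each time point".

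SPID is the sum of the PIDs, each multiplied by the hours since the preceding observation. SAP Appendix A item 6 states: "The SPID at 4, 6, 8, and 24 hours post-dose will be calculated". SAP section 8.3 sets scores after the first rescue dose to missing and, apart from the three TOTPAR endpoints, says that "no imputations will be performed to replace missing values for any of the other endpoints".

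**The concern.** SPID24 is the only SPID that extends past 8 hours, and the 16-hour score is the only pain intensity reading between 8 and 24 hours. On the listed times that score drops out. One reading at 24 hours then stands for the whole period from 8 to 24 hours, and a difference between arms at 16 hours adds nothing to SPID24.

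The texts also allow more than one calculation. A programmer who follows the PID list and one who follows the wording on every time point would produce different SPID24 values from the same data. The SAP does not say which applies, so the choice could be made after results are known.

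The scope is limited to SPID24, the by-time PID table and, possibly, peak PID and time to peak PID, which are taken over 24 hours (SAP Appendix A items 7 and 12).

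**Working it through.** **Inputs.** The weighting rule is in protocol section 12.2.1.4 and SAP Appendix A item 6: weight = time of the reading minus time of the preceding one. The common times up to 8 hours are 0.25, 0.5, 0.75, 1, 1.5, 2, 3, 4, 5, 6, 7 and 8.

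**Check of the rule on a stated figure.** Protocol section 7.1 and SAP section 8.1.1 give a TOTPAR4 maximum of 16. The weights up to 4 hours are 4 × 0.25 + 2 × 0.5 + 2 × 1 = 4, and 4 hours × 4 points = 16. The rule reproduces the stated figure. The documents give no corresponding figure for SPID24.

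**Weights for SPID24.** Up to 8 hours they are 4 × 0.25 + 2 × 0.5 + 6 × 1 = 8. After that:

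| Reading of the text | Weight at 16 h | Weight at 24 h | Sum | Share on 24 h | Maximum for a baseline of 7 |
|---|---|---|---|---|---|
| Listed times only | none | 24 − 8 = 16 | 24 | 16/24 = 66.7% | 7 × 24 = 168 |
| 16 h counts as the preceding observation, but its PID is not summed | none | 24 − 16 = 8 | 16 | 8/16 = 50% | 7 × 16 = 112 |
| 16 h included | 8 | 8 | 24 | 8/24 = 33.3% | 7 × 24 = 168 |

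The ±6 minute windows at 8 and 24 hours move the first share only between (23.9 − 8.1)/23.9 = 66.1% and (24.1 − 7.9)/24.1 = 67.2%.

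**Effect on one subject.** Listed times minus 16 hours included = 16 × PID24 − (8 × PID16 + 8 × PID24) = 8 × (PID24 − PID16). Each 1-point gap moves SPID24 by 8 points, which is 8/168 = 4.8% of the maximum for a baseline of 7.

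**Effect on the comparison of arms.** An arm difference of d points at 16 hours contributes 8d to SPID24 if the reading is included and 0 if it is not.

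**Precision (illustration only).** Assume complete data, the same SD at every time and a common correlation ρ between PIDs. Then SD(SPID24) = SD × √[(1 − ρ) × Σw² + ρ × (Σw)²]. The sum of squared weights up to 8 hours is 4 × 0.0625 + 2 × 0.25 + 6 × 1 = 6.75. On the listed times Σw² = 6.75 + 256 = 262.75. With 16 hours included it is 6.75 + 64 + 64 = 134.75. In both cases (Σw)² = 24² = 576. At an assumed SD of 2.5:

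| ρ | Listed times | 16 h included | Reduction in SD |
|---|---|---|---|
| 0.3 | 47.2 | 40.9 | 13.5% |
| 0.5 | 51.2 | 47.1 | 7.9% |
| 0.7 | 54.9 | 52.7 | 4.1% |

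The percentage reductions do not depend on the SD.

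**The case against.** The strongest reply is that the SPID definition does not refer to the PID list. It sums over observations, the 16-hour score is an observation, and two sections plan PID at every time point. Read that way, the 24-hour weight is already 8/24, and the defect is only an inconsistent list. This stands in part: two thirds holds on the listed times and is not the only reading. But the explicit lists in both documents then contradict the intended calculation and need the same edit.

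Several further points are fair:

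- Two thirds is a share of time weight, not of the SPID24 value, which depends on the scores.
- The middle row of the weight table is a strained reading, and the 112-point maximum depends on it.
- Leaving PID16 out of the by-time table loses little. Pain intensity at 16 hours is analysed with adjustment for baseline, and the PID contrast is the same contrast with the sign reversed.
- SPID24 is one of several secondary endpoints without multiplicity adjustment, and any weighting would apply equally to all arms.
- The SD figures rest on assumptions, and a lower SD alone does not prove a gain in power, because including 16 hours can also change the arm difference.
- The weighting formula already handles a missing 16-hour score. What remains open is a missing or post-rescue 24-hour score, a gap that the 16-hour omission does not cause.

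The omission might also be deliberate. The score is recorded at home, the third dose is due at 16 hours ± 1 hour, and the documents do not say which comes first. The question whether pain is at least half gone also skips from 8 to 24 hours. But no rationale is given. The half-gone question is not asked at 16 hours, whereas the NRS is. The SAP also runs peak pain relief to 16 hours, so it does not treat that assessment as unusable. Under backward weighting, a 16-hour score standing for 8 hours is less of a stretch than a 24-hour score standing for 16.

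**Conclusion.** The concern holds. The PID lists in both documents omit a time at which pain intensity is collected, and they conflict with the plan to analyse PID at every time point. On the listed times, the 24-hour reading carries 66.7% of the SPID24 time weight instead of 33.3%, and the 16-hour score is discarded. These shares follow directly from the plan's own rule at the scheduled times and need no outside assumption. The maxima use an illustrative baseline of 7, and the SD reductions use an assumed common SD and correlation.

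The trial's primary conclusion is not at risk. The point should still be settled before unblinding, because a listed secondary endpoint can at present be calculated in more than one way.

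**What to change.** Before unblinding:

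1. Add 16 hours to the PID lists in protocol section 12.2.1.4 and SAP Appendix A item 5. If the protocol is not reopened, record the difference in SAP section 11.
2. State in SAP Appendix A item 6 that SPID24 = SPID8 + 8 × PID16 + 8 × PID24.
3. Add a rule for incomplete scores. For example, if only the 16-hour score is missing, the 24-hour PID takes the 16-hour weight, as the formula implies. If the 24-hour score is missing or falls after rescue medication, say whether SPID24 is set to missing, and report the number of such subjects per arm.

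The cost is two list edits and one or two SAP sentences, with no new data collection. The one drawback is that SPID24 would depend on a further score, recorded at home on paper, which can be missing. Item 3 covers that.
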